3.1.5 Pharmaceutical Data

See **section 3.2.3** for oxaliplatin pharmaceutical data.

3.1.6 Administration

cGMP-certified $[^{14}\text{C}]$ oxaliplatin drug product, already in aqueous solution (0.5 mg/mL), is in sterile, single-use vials that will be stored at the UC Davis Investigational Drug Service. This $[^{14}\text{C}]$ oxaliplatin is ready to use, and no reconstitution is needed. Nuclear medicine and oncology and physicians will calculate the $[^{14}\text{C}]$ oxaliplatin dose and the unlabeled oxaliplatin dose to obtain a patient specific microdose of $[^{14}\text{C}]$ oxaliplatin. When the two drugs are combined during infusion, a microdose is created at the desired radiochemical specific activity and chemical dose (see **section 6.3.1**). The $[^{14}\text{C}]$ oxaliplatin infusion mixture will be prepared by a nuclear medicine technician by adding the $[^{14}\text{C}]$ oxaliplatin to an infusion bag containing D5W solution. The unlabeled

oxaliplatin infusion mixture will be prepared by the infusion pharmacy at UC Davis Cancer Center by adding the unlabeled oxaliplatin to a separate infusion bag containing D5W solution. Both unlabeled and ^{14}C -labeled oxaliplatin will be concurrently infused intravenously over 2 hours at the UC Davis Cancer Center Infusion Center. A chemotherapy nurse will administer the unlabeled oxaliplatin. A Nuclear Medicine Technologist (CNMT) will administer the ^{14}C -labeled oxaliplatin via Y-site connection to the unlabeled oxaliplatin.

3.1.7 Storage and Stability

[^{14}C]oxaliplatin Solution (0.5 mg/mL in water for injection) is packaged as a sterile, pyrogen-free, 1.0 mL solution in single use, clear 2 mL glass vials with a rubber cap. It will be stored at the UC Davis Investigational Drug Service in a -20°C freezer. It is stable when stored at -20°C. High performance liquid chromatography (HPLC) will be performed with the [^{14}C]oxaliplatin at 6-month intervals to confirm its stability throughout this trial.

3.1.8 Manufacture and Formulation

[^{14}C]oxaliplatin drug substance was manufactured at GE Healthcare using organic chemical synthesis, therefore, free of viral or prion contamination. The specific activity of the stock [^{14}C]oxaliplatin is 54 mCi/mmol. The purity is 97.7% as determined by HPLC. The investigational [^{14}C]oxaliplatin solution (the drug product) will be formulated in water for injection and processed at the UC Davis cGMP facility for sterile filtration, bacteriostasis/ fungistasis tests, endotoxin testing, following cGMP manufacturing procedures. The cGMP [^{14}C]oxaliplatin for injection solution is stored at UC Davis Investigational Drug Service and ready for the clinical trial. The identity, strength, purity, and stability analyses are performed at Moravek Radiochemical Inc (Brea, CA). Upon thawing, vials will be visually inspected for the presence of particulate matter. Vials with observable particulates will be rejected.

3.2 Standard of Care Drug Information

3.2.1 5-Fluorouracil (5-FU)

a. Description

1. 5-FU is a fluorinated pyrimidine, which has been modified from the naturally occurring product uracil by the addition of a fluoride at position 5.
2. Molecular Formula: $\text{C}_4\text{H}_3\text{FN}_2\text{O}_2$
3. Molecular Weight: 130.1g/mol

b. Pharmacology

Mechanism of Action: 5-FU's primary mode of action is the inhibition of thymidylate synthase which is necessary for both the synthesis and repair of DNA. The agent exhibits activity in different phases of the cell cycle based on mode of administration. After bolus exposure of 5-FU s-phase cytotoxicity is noted. After 24 hours of continuous intravenous infusion G-1 phase cytotoxicity has been demonstrated.

c. Pharmacokinetics

1. Absorption: Oral 5-FU is incompletely absorbed from the GI tract with highly variable rates of bioavailability reported between 0 and 80%. Topical absorption

is also minimal with only 2.4% of active drug being absorbed from the 5% commercial cream.

2. Distribution: 5-Fluorouracil has wide ranging distribution to both tissue and extracellular fluid. Volume of distribution has been reported between 13-27 liters after IV bolus administration.

3. Metabolism: The metabolism of 5-FU is well known and occurs primarily in the liver via non-linear kinetics. The rate limiting step of hepatic breakdown is the conversion of 5-fluorouracil to 5-6 dihydrofluorouracil via dihydropyrimidine dehydrogenase (DPD). Patients with known DPD deficiency should not be given 5-FU.

4. Elimination: the elimination half-life of 5-FU after IV bolus administration has been reported to occur within 6-22 minutes. Small amounts of unchanged 5-FU are eliminated via the kidney and biliary systems.

d. Adverse Effects

1. Human:

- CNS: confusion, disorientation, euphoria, nystagmus, headache, encephalopathy, and peripheral neuropathy
- Ophthalmic: lacrimal duct stenosis, visual changes, lacrimation, and photophobia, excessive nasal discharge, reddening of the eyes, blurring of the vision
- Gastrointestinal: stomatitis, esophagopharyngitis, nausea, vomiting, anorexia, diarrhea, gastrointestinal ulceration and bleeding
- Cardiovascular: cardiomyopathy, ischemic chest pain, myocardial ischemia, diaphoresis, thrombophlebitis, electrocardiogram changes.
- Dermatologic: maculopapular rash, alopecia, dry skin, fissuring, hand-foot syndrome, nail changes, rash, photosensitivity and vein pigmentation. onycholysis, dystrophy, pain and thickening of the nail bed, transverse striations, half and half nail changes, loss of nail, paronychial inflammation, and hyperpigmentation
- Hematologic: leucopenia, agranulocytosis, anemia, epistaxis, pancytopenia, and thrombocytopenia
- Immunologic: allergic reactions, anaphylaxis

2. Pregnancy and lactation: 5-FU is classified as pregnancy category D.

Teratogenic effects have been demonstrated in animals, however no well controlled studies in humans have been performed. In addition, no adequate data is available on the use of 5-FU while breast feeding. Women are advised to use formula if remaining on treatment.

e. Administration (Dosing): See treatment plan, **section 6.5**

f. Storage/Stability

1. Compatibility: Store unopen vials at room temperature and protect from light. May be diluted in NS or D5W.

2. 5-FU is a cytotoxic drug and appropriate procedures for handling, preparing and administering the drug should be followed.

3. When diluted in NS or D5W to a concentration of 1.5 mg/ml in either glass or polyvinyl chloride containers 5-FU is stable for 8 weeks at room temperature. In ethylene vinyl chloride pumps, 5-FU 10 mg/ml in NS or D5W is stable for 28 days at 4—35 degrees C.

g. How Supplied

5-FU is available as an IV solution for injection and will be obtained from commercial supply.

3.2.2 Leucovorin Calcium

a. Description

1. Leucovorin is a mixture of the diastereoisomers of 5-formyl derivative of tetrahydrofolic acid. The active component is the (-)-L-isomer known as Citrovorum factor.

2. Molecular Formula: $C_{20}H_{21}CaN_7O_7$

3. Molecular Weight: 511.51 g/mol

b. Pharmacology

Mechanism of Action: During normal processes, thymidylate synthetase forms a noncovalent ternary complex with deoxyuridylate (dUMP) and the reduced folate cofactor of leucovorin 5,10-methylenetetrahydrofolate (mTHF). The reduced folate facilitates the association and disassociation of the complex and the formation of thymidylate (dTDP) and dihydrofolate. Fluorouracil inhibits thymidylate synthetase through the covalent binding of 5-fluorodeoxyuridine monophosphate (FdUMP) and mTHF. The binding of FdUMP is dependent upon the intracellular concentration of mTHF. Since L-leucovorin is metabolized to mTHF, it increases and stabilizes the binding of FdUMP to thymidylate synthetase, thus increasing the cytotoxic effects of fluorouracil.

c. Pharmacokinetics

1. Absorption: Oral bioavailability of leucovorin is concentration dependent and severely reduced with doses greater than 25 mg. Studies have produced bioavailabilities of 97% 75%, and 37% for doses of 25 mg, 50mg and 100mg respectively.

2. Distribution: Leucovorin is rapidly converted to mTHF and distributed widely to tissues including the CNS. Distribution is however slowed in the presence of methotrexate as this agent competes with bodily tissues for leucovorin, and a higher percentage of unchanged drug is excreted in the urine when methotrexate is present.

3. Metabolism: Through the intravenous route the active isomer of leucovorin, L-leucovorin, is primarily metabolized through hepatic means to mTHF. The d isomer is not metabolized nor biologically active. By the oral route leucovorin is converted to mTHF primarily by the intestinal mucosa.

4. Elimination: the d isomer is primarily excreted unchanged in the urine while the active form is extensively metabolized by intestinal and hepatic means. Leucovorin has a half life of approximately 6 hours.

d. Adverse Effects

1. Human toxicity:

- Gastrointestinal: Toxicity has been studied in combination with 5FU where diarrhea, dehydration and stomatitis are all more common with the combination.
- Immunologic: hypersensitivity and anaphylaxis have been reported
- Endocrine: hypocalcemia

2. Pregnancy and Lactation: Leucovorin is classified as FDA pregnancy risk category C. No adequate human studies have examined the effects of this drug on the fetus. It is not known if leucovorin is excreted into breast milk, and therefore mothers receiving the agent should consider alternative modes of feeding.

e. Administration (Dosing): See treatment plan, **section 6.5**

f. Storage/Stability

1. Compatibility Information: leucovorin may be dilute in D5W, D10W, NS, Ringer's, or lactated Ringer's solution.
2. Drug handling and compatibility: leucovorin is not considered as hazardous substance and as such may be prepared in a laminar flow hood using aseptic technique.
3. Store dry powder, reconstituted solution and tablets at controlled room temperature. Protect from light. When reconstituted with Bacteriostatic Water for Injection, the resulting solution must be used within seven days. If reconstituted with Sterile Water for Injection, use immediately and discard any unused portion. Diluted injections are stable for 24 hours.

g. How Supplied

Leucovorin is provided as both a powder and liquid for injection. Leucovorin is commercially available, and will be obtained from commercial supply for this study.

3.2.3 Oxaliplatin (Eloxatin®)

a. Description

1. Oxaliplatin is a third generation platinum analog. Oxaliplatin contains a bulky carrier ligand, 1,2-diaminocyclohexane (DACH), not present in either cisplatin or carboplatin.
2. Molecular Formula: $C_8H_{14}N_2O_4Pt$
3. Molecular Weight: 397.3 g/mol

b. Pharmacology

Mechanism of Action: Oxaliplatin is a non-cell cycle specific, alkylating antineoplastic agent that inhibits DNA synthesis through the formation of Crosslinks between the N7 positions of two adjacent guanines (GG), adjacent adenine-guanines (AG), and guanines separated by an intervening nucleotide (GNG). These crosslinks inhibit DNA replication and transcription.

c. Pharmacokinetics

1. Absorption: NA
2. Distribution: oxaliplatin has a protein binding of 70-95% with longer in vitro exposure leading to higher protein binding rates. In addition, it has been demonstrated approximately 37% of platinum is taken up by erythrocytes. Steady state volume of distribution is approximately 35L.
3. Metabolism: Oxaliplatin is rapidly metabolized in plasma primarily by biotransformation. No unchanged oxaliplatin is found 2 hours after administration. Oxaliplatin demonstrates no cytochrome P450 metabolism. 17 known metabolites of oxaliplatin have been identified, monochloro DACH platinum, dichloro DACH platinum, and mono and diaquo DACH platinum, are cytotoxic.
4. Elimination: Platinum is predominately excreted through the kidney with a clearance of 9-17 L/hour. Elimination kinetics are triphasic with alpha, beta, and gamma half-lives of approximately 25.8 minutes, 16.8 hours and 391 hours. A very small (2%) amount of platinum is excreted in the feces.

d. Adverse Effects:

1. Refer to package insert or manufacturer website for the most complete and up to date information on contraindications, warning and precautions, and adverse reactions.
 - Cardiovascular: Dyspnea, coughing, hypertension, edema, chest pain
 - Dermatology: injection site reaction
 - Gastrointestinal: Stomatitis, nausea, vomiting, taste alteration, anorexia, diarrhea, gastrointestinal reflux
 - Hematologic: leucopenia, agranulocytosis, anemia, epistaxis, pancytopenia, and thrombocytopenia, febrile neutopenia
 - Immunologic: allergic reactions, anaphylaxis
 - Hepatic/Metabolic/Laboratory/Renal: hypokalemia, dehydration
 - Neurologic: peripheral neuropathy
2. Pregnancy and Lactation: Oxaliplatin may cause fetal harm when administered to a pregnant woman (FDA pregnancy risk category D). In animal studies, oxaliplatin at doses less than one-tenth the recommended human dose based on body surface area caused developmental mortality and adversely affected fetal growth (decreased fetal weight, delayed ossification). If this drug is used during pregnancy or if the patient becomes pregnant while taking this drug, the patient should be counseled regarding the potential risks to the fetus. Females of childbearing potential should avoid becoming pregnant while receiving treatment with oxaliplatin. It is unknown whether oxaliplatin is excreted in breast milk. Therefore alternative means to feeding, or delaying treatment should be considered.

e. Administration (Dosing): See treatment plan, **section 6.5**

f. Storage/Stability

1. Compatibility: Oxaliplatin is incompatible in a solution with alkaline medications or diluents (such as basic solutions of 5-FU) and must not be mixed with these or administered simultaneously through the same infusion line. The infusion line should be flushed with D5W prior to administration of any concomitant medications. Only D5W is acceptable for dilution. Aluminum needles or iv sets should not be used as degradation of platinum may occur.
2. Special Handling: oxaliplatin is a cytotoxic drug and appropriate procedures for handling, preparing and administering the drug should be followed.
3. Store the intact vials at controlled room temperature. Excursions permitted to 15°C to 30°C (59°F to 86°F), not exceeding 30°C. Reconstituted solution: in 5% Dextrose or Water for Injection in the original vial, the solution may be stored for up to 48 hours between 2°C to 8° C (36°F-46°F). Infusion solution: after dilution in 5% Dextrose in Water, the shelf life is 24 hours at 2°C to 8°C (36°F-46°F).

g. How Supplied

1. Oxaliplatin is commercially available and will be obtained from commercial supply.

4 ELIGIBILITY CRITERIA

4.1 Inclusion Criteria

- 4.1.1 Histologically or cytologically confirmed colon, rectal, pancreatic, gastroesophageal, appendiceal, or small bowel adenocarcinoma.
- 4.1.2 Intent to treat the patient with a FOLFOX chemotherapy regimen containing 5-FU, leucovorin, and oxaliplatin according to clinical standard practice. The intent should be to dose oxaliplatin at 85 mg/m² on an every 2 week basis.
- 4.1.3 Treatment with any additional FDA-approved biologic agent (i.e. bevacizumab, cetuximab, or panitumumab) is allowed according to standard practice.
- 4.1.4 Prior radiation or surgery is allowed, but should be finished at least 2 weeks prior to study enrollment.
- 4.1.5 Any number of prior therapies other than oxaliplatin is allowed.
- 4.1.6 Participants must be 18 years or older.
- 4.1.7 Zubrod performance status equal to or less than 2 (Karnofsky equal to or greater than 50%). See **Appendix A**.
- 4.1.8 Life expectancy of at least 3 months.
- 4.1.9 Participants must have normal organ and marrow function as defined as:
 - absolute neutrophil count greater than or equal to 1,500/microL
 - Platelets greater than or equal to 100,000/microL
 - total bilirubin less than 3 X institutional upper limit of normal (ULN)
 - AST (SGOT) less than or equal to 5 X ULN
 - creatinine less than 1.5 X ULN
- 4.1.10 Women of child bearing potential must not be pregnant. A pre-study pregnancy test must be negative.
- 4.1.11 Women of child-bearing potential must agree to use adequate contraception (hormonal or barrier method of birth control; abstinence) prior to study entry and for 30 days after study participation.
- 4.1.12 Men must agree to use adequate contraception (barrier method or abstinence) prior to study entry and for 30 days after study participation.
- 4.1.13 Ability to understand and willing to sign a written informed consent document.

4.2 Exclusion Criteria

- 4.2.1 Prior treatment with oxaliplatin.
- 4.2.2 Patients must not receive concomitant radiation.
- 4.2.3 Uncontrolled intercurrent illness including, but not limited to, ongoing or active infection, symptomatic congestive heart failure, unstable angina pectoris, cardiac arrhythmia, or psychiatric illness/social situations that would limit compliance with study requirements.

- 4.2.4 Participants who are pregnant or nursing.
- 4.2.5 Participants who are allergic to any platinum agent.
- 4.2.6 Participants who have more than Grade 1 peripheral neuropathy.

5 DESCRIPTIVE/STRATIFICATION FACTORS

There is no stratification for the primary analysis of this trial. However the following data will be collected for exploratory analysis of clinical, molecular and treatment factors on outcome.

- Number of prior treatments
- Time from diagnosis
- RAS and BRAF mutation status (if performed)
- ERCC1 expression (if performed)

6 STUDY DESIGN AND TREATMENT PLAN

6.1 Study Design

This is a prospective feasibility study of a [¹⁴C]oxaliplatin microdose assay to predict exposure and sensitivity to oxaliplatin as part of standard-of-care FOLFOX chemotherapy. Consenting patients who will be receiving FOLFOX as their treatment for cancer will be enrolled. Patients will receive two [¹⁴C]oxaliplatin microdose infusions over the course of the study. The first part of the study is a Phase 0 [¹⁴C]oxaliplatin microdose infusion occurring over 2 hours and followed by serial blood draws over a 24 hour period for microdose pharmacokinetic and pharmacodynamic analysis (on surrogate peripheral blood mononuclear cells). Between 2 days and 4 weeks after the administration of this phase 0 microdose, patients will begin FOLFOX therapy according to usual care. The initial treatment oxaliplatin dose will be diluted with the same amount of [¹⁴C]oxaliplatin microdose as previously administered. Repeat blood draws for pharmacokinetic assessment of both the microdose and therapeutic dose along with pharmacodynamic analysis on PBMCs will be performed over 46-48 hours (this last draw is timed for the disconnect visit of the 5-FU infusion).

6.2 Selection of Patients

Subjects will be selective from the Medical Oncology clinics at the University of California Davis Comprehensive Cancer Center, in-hospital or via outside referral. The study will be presented to potential subjects by the physician with possible assistance from a clinical research coordinator. The enrolling physician is responsible for proposing and explaining the study to the prospective subject for the consent process.

6.3 Phase 0 [¹⁴C]Oxaliplatin Microdose

6.3.1 Preparation and Administration of [¹⁴C]Oxaliplatin Microdose

The starting dose (Dose Level 1, **Table 1**) of [¹⁴C]oxaliplatin microdose to be administered in this study is 2×10^6 dpm/kg of body weight, with the total dose of both unlabeled and ¹⁴C-labeled oxaliplatin solution being 1/100th of the planned therapeutic dosage (85 mg/m²). Calculations of the therapeutic dose and microdose of oxaliplatin will use the Du Bois and Du Bois formula for BSA:

$$\text{BSA (m}^2\text{)} = 0.20247 \times \text{Height(m)}0.725 \times \text{Weight(kg)}0.425$$

The dose of [¹⁴C]oxaliplatin is calculated in the following formula using Dose Level 1 (2 X 10⁶ dpm/kg, 1% therapeutic dose):

$$2 \times 10^6 \text{ dpm/kg} \div (2.22 \times 10^9 \text{ dpm/mCi}) \div 54 \text{ mCi/mmol} \times 397 \text{ mg/mmol} = 0.0066 \text{ mg/kg}$$

The patient specific dose of [¹⁴C]oxaliplatin will be added to an infusion bag containing D5W. Unlabeled oxaliplatin will be added to a separate infusion bag also containing D5W. Both treatment dose of unlabeled oxaliplatin and ¹⁴C-labeled oxaliplatin will be concurrently infused intravenously over 2 hours at the UC Davis Cancer Center Infusion Center. When these two infusion bags are concurrently administered to a patient, together they achieve a total final oxaliplatin microdose of 1% of the therapeutic dose. A chemotherapy nurse will administer the unlabeled oxaliplatin. A Nuclear Medicine Technologist (CNMT) will administer the ¹⁴C-labeled oxaliplatin via Y-site connection to the unlabeled oxaliplatin.

As an example, a patient with a height of 1.7 m and a body weight of 75 kg will have a BSA of 1.86 m². This patient would be planned to receive a therapeutic oxaliplatin dose of 158 mg (85 x 1.86). This patient's microdose would then be 1.58 mg of total oxaliplatin containing 1.08 mg of unlabeled oxaliplatin for injection and 0.50 mg [¹⁴C]oxaliplatin solution. The above dosing calculation should be modified as appropriate for the other dose levels in **Table 1**. [name], [name] or their designees are the only authorized prescribers for the microdosing formulation. If the designee signs the pharmacy order form in [name] or [name] absence, the designee must notify [name] or [name] as soon as possible before dosing the patient.

After the oxaliplatin infusion mixtures are prepared, the shelf-life is 6 hours at room temperature [20-25°C] or up to 24 hours under refrigeration [2-8°C]. The oxaliplatin microdose infusion mixtures should be administered concurrently through a 120-minute intravenous infusion.

6.3.2 Modification of the radioactive microdose during the study

We will vary the radioactive dose of [¹⁴C]oxaliplatin (dpm/kg) in the patient's microdose by combining the [¹⁴C]oxaliplatin with unlabeled oxaliplatin until the desired radioactive dose and chemical microdose (total dose at 1/100th of the therapeutic dose) are obtained. This effectively varies the radiochemical specific activity of the microdose infusion. The dose of [¹⁴C]oxaliplatin (dpm/kg) for this feasibility study will be determined by measuring the ¹⁴C associated with genomic DNA isolated from patient's PBMCs after microdosing. A ¹⁴C signal 10-100 times background is acceptable for this study. Of note, the sensitivity for pharmacokinetic analysis is much higher and we do not expect dose modification to have any impact on pharmacokinetic feasibility.

We will start [¹⁴C]oxaliplatin at 2 X 10⁶ dpm/kg of body weight, and add unlabeled oxaliplatin to 1% of the therapeutic oxaliplatin as calculated based on the dose of 85 mg/m². This dose level was demonstrated to be adequate and safe in a single breast cancer patient in a prior study. Two patients will be recruited to this dose level (Dose

Level 1). If the ^{14}C signal in PBMC genomic DNA is sufficient, dose level 1 will be used for the rest of the study. If the ^{14}C signal is insufficient or too high, the dose level will be titrated up or down, respectively, based on the ^{14}C signal as outlined in **Table 1**, and administered to two additional patients per dose level until a sufficient ^{14}C signal is obtained. If no ^{14}C signal can be detected in the genomic DNA at Level 3, no further escalation will be performed.

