2.6 Assessment of Microdose-induced Oxaliplatin-DNA damage

Several studies have confirmed that the levels of drug-DNA adducts directly correlate with the outcomes of platinum-based chemotherapy, particularly in peripheral blood mononuclear cells (PBMC). After Pt-based chemotherapy, DNA adducts can be detected in multiple tissues [10, 71, 72]. The concentration of Pt-DNA adducts correlates to the drug concentration and incubation time in cell culture [10]. Decreased Pt-DNA adducts are associated with resistance to Pt chemotherapy in cell lines [73]. The levels of DNA adducts, as detected by immunohistochemical staining, correlated with response to Pt chemotherapy [71, 72]. Those patients with low drug-DNA adducts or increased repair of drug-DNA adducts had worse outcomes [74]. Oxaliplatin-DNA adducts have been measured by Pieck et al [75] in peripheral blood lymphocytes from 37 patients with a variety of malignancies. In patients showing tumor response, adduct levels after 24 and 48 h were significantly higher than in nonresponders, indicating that drug-DNA adduct levels in surrogate tissues may serve as biomarkers of response. However, the commonly used drug-DNA adduct detection methods such as atomic absorption spectroscopy, Southern blot, or immunological detection with antibodies, are not sufficiently sensitive for detection of drug-DNA adducts induced by microdose concentrations of platinum drugs. Cell lines and patients need to be exposed to chemotherapeutic doses (high, toxic concentrations) for a sufficient number of drug-DNA adducts to be created for the common adduct detection methods above to be informative [76]. Therefore, these traditional approaches can ONLY identify chemoresistance in patients AFTER full-dose chemotherapy.

In this study, we will adopt the highly sensitive technology of AMS for detection of microdose-induced platinum-DNA adducts. We have shown that AMS is about 1000 times

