3.1.3 Dosage

The dose of ^{14}C oxaliplatin to be administered as a microdose may need to be modified (see **section 6.3.2**) based on the ^{14}C signal in genomic DNA isolated from patients after receiving one of the dose levels identified in the dose titration table (**Table 1**). The dose levels being evaluated were identified using the following rationale: Based on our ongoing clinical microdosing trial with ^{14}C carboplatin, the radioactive dose of ^{14}C carboplatin is 10^7 dpm/kg of patient body weight with a total carboplatin of 1% of therapeutic carboplatin with AUC of 6. Our pre-clinical studies with oxaliplatin dosing of cell lines indicate that the requirement for ^{14}C oxaliplatin is about 10 times less than ^{14}C carboplatin. We will begin this study at dose level 1, which we have already

demonstrated to be adequate and safe in a single breast cancer patient. Therefore, the start dose (Dose Level 1) of [¹⁴C]oxaliplatin will be 2×10^6 dpm/kg of body weight with the total oxaliplatin at 1% of therapeutic dose (**Table 1**). Based on the ¹⁴C signal in genomic DNA of peripheral blood mononuclear cells (PBMC) in patients after dosing with this dose level 1, the dose will be titrated up or down, if needed, and administered to separate patients with the goal of achieving a ¹⁴C signal at 10-100 times the background. Instructions for preparing the microdose formulation are presented in **section 6.3.1**.

Table 1. Dose titration table

Dose levels	[¹⁴ C]oxaliplatin (dpm/kg of body weight)	Total oxaliplatin (% of therapeutic dose)
-1	1×10^6	1%
1	2×10^6	1%
2	2×10^6	3%
3	10×10^6	3%

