3.1.4 Human Toxicity

3.1.4.1 Oxaliplatin Chemical Toxicity.

In this diagnostic feasibility study, patients will receive a small microdose of ¹⁴C-labelled oxaliplatin (1% of therapeutic dose, or less than 3 mg). We do not expect to see any of the clinical side effects associated with standard dose oxaliplatin chemotherapy to occur at this low dose. The most common side effects of standard dose oxaliplatin chemotherapy are presented in **section 3.2.3**.

3.1.4.2 Radiation Toxicity Due to ¹⁴C-label.

Patients will receive minimal radiation exposure (<0.02 mSv) with no expected toxicity.

Drug metabolism with ¹⁴C-labeled drugs using AMS has been studied in healthy volunteers without significant toxicities [77, 78]. We have calculated the radiation dose each patient will receive if he/she participates in this trial. Most oxaliplatin is excreted in urine. The decline of ultrafilterable platinum levels following oxaliplatin administration is triphasic, characterized by two relatively short distribution phases ($t_{1/2\alpha}$ of 0.43 hours and $t_{1/2\beta}$ of 16.8 hours) and a long terminal elimination phase($t_{1/2\gamma}$ of 391 hours). We use 16.8 hours as the half-life for calculation.

For the starting dose, each patient will receive [¹⁴C]oxaliplatin at 2×10^6 dpm/kg of body weight.

$$1 \mu\text{Ci} = 2.22 \times 10^6 \text{ dpm}$$

If the patient's body weight is 75 kg, the total radiation dose *per microdose* will be:

$$2 \times 10^6 \text{ dpm/kg} \times 75 \text{ kg} = 1.5 \times 10^8 \text{ dpm} = 67.6 \mu\text{Ci} \text{ per microdose.}$$

$$1 \mu\text{Ci} = 2.22 \times 10^6 \text{ dpm} \times 0.049 \text{ MeV/disintegration} = 108,780 \text{ MeV/min} = 108,780 \text{ MeV/min} \times (1.6 \times 10^{-13} \text{ joules/Mev}) = 1.74 \times 10^{-8} \text{ joules/min}$$

Therefore, each patient will receive:

$$67.6 \mu\text{Ci} \times (1.74 \times 10^{-8} \text{ joules/min} \cdot \mu\text{Ci}) = 1.2 \times 10^{-6} \text{ joules/min per microdose.}$$

If the average body weight is 75 kg, the radiation dose for each microdose will be:

$$1.2 \times 10^{-6} \text{ joules/min person} \times \text{person} / 75 \text{ kg body weight} = 1.6 \times 10^{-8} \text{ joule/min/kg}$$

We propose that, after 5 half-lives (84 hours), the $[^{14}\text{C}]$ oxaliplatin remaining in the body will be negligible. If the patient is continuously exposed to $[^{14}\text{C}]$ radiation without metabolism of $[^{14}\text{C}]$ oxaliplatin, the radiation dose will be:

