$$1.6 \times 10^{-8} \text{ joule/min/kg} \times 60 \text{ min/hr} \times 84 \text{ hr (five half-lives)} = 7.9 \times 10^{-5} \text{ joules/kg}$$

$$1 \text{ joule/kg} = 1 \text{ Sv}$$

The radiation exposure for each microdose will be 7.9×10^{-5} Sv or 0.079 mSv. The radiation exposure for each patient completing both microdoses will be 0.016 mSv.

If this study ends up at Dose Level 3 (10×10^6 dpm/kg, or 5 times the radiation dose used to calculate the above radiation exposure. **Table 1**), and patients undergo both microdose administrations, the radiation exposure will be $0.079 \text{ mSv} \times 5 \times 2 = 0.79 \text{ mSv}$.

The annual effective radiation dose equivalent from natural internal sources is 1.6 mSv per person. The radiation exposure for an abdominal CT scan is 10 mSv. **The radiation exposure to $[^{14}\text{C}]$ oxaliplatin for a patient completing both microdoses on this study is $0.016 \text{ mSv} \div 10 \text{ mSv} = 0.16\%$ of an abdominal CT scan.**

Here, we assume that patients are exposed to $[^{14}\text{C}]$ oxaliplatin radiation at the initial dose for 84 hours without correcting the calculation for reduction of the *in vivo* drug concentration drug by excretion, which makes this a very conservative calculation.

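### Level 2 of Table 1, the first step up for a weak ¹⁴C signal, leaves the ¹⁴C dose unchanged, and the 1% and 3 mg statements fail where the table sets 3%

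*Combined protocol and SAP*

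**What the plan says.** Section 6.3.2 (protocol) presents the titration as a change in radioactive dose. Labelled and unlabelled drug are mixed "until the desired radioactive dose and chemical microdose (total dose at 1/100th of the therapeutic dose) are obtained", and the dpm/kg for the study is set from the ¹⁴C found in PBMC genomic DNA. A signal of 10 to 100 times background is acceptable. Two patients start at Level 1. If their signal is insufficient or too high, "the dose level will be titrated up or down, respectively", following Table 1, with two more patients at each level tried.

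Table 1 (Section 3.1.3) sets:

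| Level | dpm/kg | Total oxaliplatin |
|---|---|---|
| -1 | 1×10⁶ | 1% |
| 1 | 2×10⁶ | 1% |
| 2 | 2×10⁶ | 3% |
| 3 | 10×10⁶ | 3% |

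Section 3.1.4.1 describes the chemical exposure as "1% of therapeutic dose, or less than 3 mg", without reference to level. The radiation text in Section 3.1.4.2 does cover escalation, in the sentence that begins "If this study ends up at Dose Level 3". Section 6.3.1 works a Level 1 example and adds that the calculation "should be modified as appropriate for the other dose levels in" Table 1.

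**The concern.** An escalation step should move the quantity that was found too low. AMS counts ¹⁴C only, so unlabelled drug adds adducts that the assay cannot see and dilutes the label. Level 2 adds only unlabelled drug. In a study sized at six evaluable patients, two could be spent on a step that the documents give no reason to expect will raise the signal, before Level 3 raises the ¹⁴C dose 5-fold.

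The same two levels carry a chemical dose that the safety text does not describe and that the 1/100th wording in Section 6.3.2 excludes. Enforcing 1/100th would make Level 2 identical to Level 1.

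**Working it through.** **Inputs.** From Section 6.3.1: the BSA formula, 85 mg/m², the conversion of dpm/kg to mg/kg, and the example patient (1.7 m, 75 kg). Dose levels are from Table 1, vial content from Section 3.1.7, and the radiation method from Section 3.1.4.2.

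**Reproducing the protocol's Level 1 example.**
- BSA = 0.20247 × 1.7^0.725 × 75^0.425 = 1.8635 m² (protocol: 1.86).
- Therapeutic dose = 85 × 1.8635 = 158.4 mg (protocol: 158). 1% = 1.584 mg; 3% = 4.752 mg.
- Labelled drug = 2×10⁶ ÷ 2.22×10⁹ ÷ 54 × 397 = 0.00662 mg/kg (protocol: 0.0066); × 75 = 0.497 mg (protocol: 0.50).

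The example is reproduced.

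**Other levels, same patient.**

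| Level | Labelled, mg | Total, mg | Labelled fraction |
|---|---|---|---|
| 1 | 0.497 | 1.584 | 31.4% |
| 2 | 0.497 | 4.752 | 10.5% |
| 3 | 2.484 | 4.752 | 52.3% |
| 4×10⁶ dpm/kg at 1% (possible replacement for Level 2) | 0.993 | 1.584 | 62.7% |

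**Signal relative to Level 1.** Take labelled and unlabelled drug as interchangeable, which is the tracer assumption of the assay. Let F be the fold rise in total adducts over Level 1. Relative signal = F × (labelled fraction ÷ 31.4%).
- Level 2: F × 10.5/31.4 = F/3.0. If F = 3 (proportional), the ratio is 1.0; if F = 2, 0.67; doubling needs F = 6.
- Level 3: F × 52.3/31.4 = 1.67F, which is 5.0 at F = 3.
- 4×10⁶ at 1%: the chemical dose is unchanged, so F = 1 whatever the shape of the dose-adduct relation, and the ratio is 62.7/31.4 = 2.0.

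**The 3 mg statement.** A 3% total exceeds 3 mg when BSA > 3 ÷ (0.03 × 85) = 1.18 m². In the example it is 4.75 mg, which is 1.75 mg above the stated limit and 3.17 mg above the 1% dose.

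**The 1/100th statement.** At Level 3 the labelled drug alone (2.484 mg) exceeds the 1% total (1.584 mg). A 1% total can hold at most 10×10⁶ × 1.584/2.484 ≈ 6.4×10⁶ dpm/kg in this patient, so setting the whole table to 1% would not work either. A dose of 4×10⁶ dpm/kg fits within 1% up to about 169 kg at 1.7 m (144 kg at 1.5 m, 207 kg at 2.0 m).

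**Radiation by the protocol's method.** At 2×10⁶ dpm/kg, 0.079 mSv per microdose, so 0.158 for two. Section 3.1.4.2 prints 0.016 mSv for two, which is not 2 × 0.079; the product is used here. At 4×10⁶, 0.316 for two. At Level 3, 0.79 for two, as printed.

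**The case against.** The documents give reasons not to expect escalation. Level 1 is reported as adequate in one earlier patient. Section 3.1.3 also says that oxaliplatin needs about one tenth of the label used for carboplatin (10⁷ dpm/kg), that is about 10⁶, and Level 1 is twice that. If escalation does happen, Level 3 is still available, and Section 11.2.2 declares the adduct analyses hypothesis-generating. This stands and limits the weight of the point. It does not explain why the table contains a step that leaves the ¹⁴C dose where it was.

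The 1/100th wording is close to editorial. Sections 6.3.1 and 6.3.2 both send the prescriber to Table 1, so a reader should not infer that the dose to be given is seriously in doubt. This also stands.

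Section 6.3.2 speaks of titrating the dose level, which has a chemical component as well as a radioactive one, and more drug could form more adducts. A reader might go the other way and infer that Level 2 is futile. The documents do not support that: they do not give the dose-adduct relation at these doses, and a more-than-proportional rise is not excluded. They do not argue for one either. Section 2.6 says only that "The concentration of Pt-DNA adducts correlates to the drug concentration and incubation time in cell culture".

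A reader might also infer a toxicity risk. The extra 3.17 mg is about 2% of the 158 mg due 2 days to 4 weeks later, and nothing in the documents suggests harm from it.

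**Conclusion.** The point holds and is conditional. Level 2 does not act on the variable that Section 6.3.2 says is titrated. Its signal exceeds that of Level 1 only if adducts rise more than 3.0-fold for a 3-fold dose, and under proportional formation the signal is unchanged. This rests on the tracer assumption and on the protocol's own formulas. Separately, and without any such assumption, the 1% and 3 mg statement in Section 3.1.4.1 is wrong at the 3% levels for BSA above about 1.18 m², and the 1/100th total in Section 6.3.2 cannot be met at Level 3 in the example.

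The consequence arises only if the Level 1 signal is insufficient. About two patients would then receive Level 2, with a phase 0 dose above the one that the safety section states. The secondary adduct data and the accuracy of the safety text are affected. It would be wrong to read this as a threat to the primary endpoint: AUC is compared after dose normalisation, and Section 6.3.2 expects no effect of dose modification on pharmacokinetic feasibility. The correction should be made, but the trial's main conclusion does not depend on it.

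**What to change.** 1. Change the Level 2 row of Table 1 to an intermediate ¹⁴C dose, for example 4×10⁶ dpm/kg at 1% total. The expected signal is about twice that of Level 1 whatever the dose-adduct shape. With the signal taken net of background, doubling brings a Level 1 result of 5 to 10 times background into the acceptable range (10 ÷ 2 = 5); a weaker one would still need Level 3.
2. In Section 6.3.2, replace the 1/100th parenthesis with *total dose per Table 1*.
3. In Section 3.1.4.1, give the chemical dose for each level of the revised table: 1% at Levels -1, 1 and 2; 3%, about 4.75 mg in the example, at Level 3 only. If Level 2 is instead kept at 3% with a higher dpm/kg, list it with Level 3. The three edits must be made together so that they agree.

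The cost is one table row and two text edits in an amendment, with no added patients or procedures. The drawback is labelled drug: 4×10⁶ dpm/kg uses twice the amount of Level 1 per microdose. With 0.5 mg vials the example patient needs two instead of one (0.993 against 0.497 mg); Level 3 needs five. One vial covers Level 1 only up to about 75.5 kg (0.5 ÷ 0.00662), so heavier patients need more at either dose. The documents do not state the supply. Radiation for two microdoses would be about 0.32 mSv, against 0.16 at Level 1 and 0.79 at Level 3.
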